#### 20.4.4.2 Early Success Interim Analysis for the Main Study Phase

An interim analysis will be performed for claiming early trial success in Wave II when 30 subjects in the PP-Wave II analysis set reach full 12-month of follow-up and all subjects in the mITT-Wave II analysis set reach three months of follow-up. At this interim, the trial will declare early success if both safety and effectiveness objectives are met:

1. The posterior probability of the safety rate being less than 14% is greater than 0.975
2. The posterior probability of the effectiveness proportion  $p_E$  being greater than 50% is greater than 0.9975.

#### **For Primary Safety Endpoint:**

The primary safety endpoint analysis performed at this interim will include 3-month safety follow-up for all mITT-Wave II subjects and will be the same as the final safety endpoint analysis.

A beta-binomial model with a non-informative uniform prior will be used for the primary safety rate. The uniform prior for the safety rate will be updated based on the observed number of events to obtain the posterior distribution for the primary safety rate. If the posterior probability of the safety rate being less than 14% is greater than 0.975, the early success primary safety endpoint will have been met.

The null and alternative hypotheses for the safety endpoint for the early success interim analysis are:

$$H_0: \Pr(P_s < 0.14) \leq 0.975$$

$$H_a: \Pr(P_s < 0.14) > 0.975$$

### **Primary Effectiveness Endpoint**

In case early success is achieved, the study will continue to follow up the subjects for the full follow-up duration, and the primary effectiveness endpoints based on full 12-month follow-up data will be descriptively summarized in subjects in the PP-Wave II analysis set. The early success effectiveness analysis will be performed in the PP-Wave II analysis set. At the time of the early success interim analysis, the posterior distribution for the 12-month effectiveness proportion will be estimated by using the piecewise exponential model described in 20.4.4.1. Early success effectiveness will be demonstrated if the  $p_{E,0.5}$  being greater than 50% is greater than 0.9975.

For the early success interim analysis, the total number of primary effectiveness events and the total subject exposure time will be used to update the vague Gamma priors for the hazard rates and obtain posterior Gamma distributions for three segments of the effectiveness model. Next, 10,000 random hazard rates will be sampled from the posterior distribution for each segment and each triplet set of hazard rates will be used to estimate a single 12-month effectiveness rate. The posterior distribution of the 12-month rate is estimated based on the 10,000 simulated rates. Using this distribution, if the probability of the 12-month effectiveness rate being greater than 50% is greater than 0.9975 (99.75%), the trial will declare early success for the effectiveness endpoint.

The null and alternative hypotheses for the primary effectiveness endpoint for the early success interim analysis are:

$$H_0: \Pr(P_E > 0.50) \leq 0.9975$$

$$H_a: \Pr(P_E > 0.50) > 0.9975$$

where  $P_E$  is the 12-month effectiveness rate.

#### 20.4.4.3 Final Analysis for the Main Study Phase

If early success is not achieved, then the final effectiveness analysis will be based on complete follow-up data for the primary effectiveness endpoint as described in this section. If trial success is achieved at the early success interim analysis, then the final analysis for the effectiveness endpoint will involve descriptive statistics on the full follow-up effectiveness data in the MITT-Wave II and PP-Wave II analysis sets.

#### **For Primary Safety Endpoint:**

The final primary safety endpoint analysis is the same analysis performed at the early success interim as all safety data is available at the time of the early success interim look. A beta-binomial model will be used for this analysis. A non-informative uniform prior will be assumed for the primary safety proportion. The primary safety endpoint will be considered a success if

$$\Pr(P_S < 0.14) > 0.975$$

The analysis population for the primary safety endpoint will be the mITT-Wave II analysis set. If the posterior probability of the safety rate being less than 14% is greater than 0.975, then the study will be considered to have demonstrated safety of the device.

**For Primary Effectiveness Endpoint:**

If trial success is not declared at the early success interim, the final analysis for the primary effectiveness endpoint will use a beta-binomial model similar to the primary safety endpoint analysis. A non-informative uniform prior will be assumed for the primary effectiveness rate.

At the time of the final analysis, the trial will be considered a success if

$$\Pr(P_E > 0.50) > 0.9775$$

The analysis population for the primary effectiveness endpoint will be the PP-II analysis set. If the posterior probability of the effectiveness rate being greater than 50% is higher than 0.9775, the study will be considered to have demonstrated effectiveness of the device.

20.4.4.4 Handling of Missing Data

If a subject has not completed 12 months of follow-up but has had a PAE, then the subject will be considered an event for the final primary safety analysis. If a subject's follow-up time is less than 12 months and the subject has not had a PAE, then that subject will be excluded from the primary safety analysis.

For the early success interim analysis of the primary effectiveness endpoint, the subjects with incomplete follow-up data who are event free will be censored at the time of their last follow-up visit, and only their observed partial follow-up time will contribute to estimating model parameters.

For the final primary effectiveness analysis, if a subject has an effectiveness failure at any time during the evaluation period, then the subject will be considered an event. Subjects without an effectiveness failure who do not have full 12 months of follow-up will be excluded from the final primary effectiveness analysis.

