### 10.3 Subject Enrollment Disposition

- **Enrolled Subjects:** Patients who sign the ICF.
- **Excluded Subjects:** Subjects who are enrolled but never undergo insertion of the study catheter. Excluded subjects will be subjected to safety event reporting between ICF signature and date of exclusion. Subjects who signed the ICF but are found to be ineligible prior to insertion of the catheter are also considered as excluded.
- **Evaluable Subjects:** All enrolled subjects who have the study catheter inserted.
- **Discontinued Subjects:** Evaluable subjects but do not undergo ablation (i.e., no energy is delivered with the study catheter).

- Discontinued subjects will remain in follow-up for 3-months post catheter insertion.
- Wave I discontinued subjects are not subjected to the additional Wave I study assessments (esophageal, neurological and PV).
- If an SAE is reported for a discontinued subject, the subject will be followed until event resolution (with or without sequelae), stabilization, or until the event is adequately explained.
- **Lost to Follow-up Subjects:** Evaluable subjects of which contact is lost after most recent visit (despite 3 documented attempts to contact the subject).
- **Withdrawn / Early Termination Subjects:** Subjects who withdraw consent for study participation or are withdrawn by the investigator, are terminated from the study prior to completion of all follow-up visits.
- **Completed Subjects:** Enrolled subjects who have not been excluded, discontinued, withdrawn, terminated early, or lost-to-follow-up from the study prior to the final study visit.

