### 20.3.2 Wave II Analysis Sets

- **Modified Intent-To-Treat (mITT-Wave II) Analysis Set:** The mITT-Wave II analysis set will consist of enrolled Wave II main study phase subjects who meet eligibility criteria and have had insertion of the study catheter—Subjects in this analysis set who are discontinued due to:
  - study catheter related reasons will be considered acute effectiveness failures
  - non-study catheter related reasons (other equipment, pump, anatomy that precludes treatment with the study catheter or commercially available catheter) will be excluded from the effectiveness analysis.
- **Full Analysis set (FAS-Wave II):** The FAS-Wave II Analysis Set will consist of all enrolled Wave II main study phase subjects who have had insertion of the study catheter (with or without delivery of PFA).
- **Per Protocol (PP-Wave II) Analysis Set:** The PP-Wave II analysis set will consist of Wave II main study phase subjects who satisfy the following criteria:
  - are enrolled and without major protocol deviations that would affect the integrity of the data
  - have undergone ablation (PFA) with the study catheter
  - are treated for the study-related arrhythmia
  - did not require the use of a non-study catheter for Pulmonary Vein Isolation (PVI)
  - did not require ablations outside the PV region
- **Roll-In Analysis Set:** The Roll-In analysis set will include all subjects who are enrolled in the roll-in phase. All endpoints will be analyzed for the roll-in analysis set separately.

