Analysis of the primary safety endpoint will be performed using the final sample size that is selected adaptively based on the primary effectiveness endpoint. All sample sizes from the interim sample selections will provide greater than 80% power for the primary safety endpoint assuming a PAE composite rate of  $\leq 7\%$  and a performance goal of 14%.

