7.4.3 Handling of Missing Data

Missing data will be queried for reasons and will not be imputed.

For the primary safety analysis, if a subject's follow-up time is less than 3 months and the subject has not had a PAE, then that subject will be excluded from the primary safety analysis.

For the primary effectiveness analysis, subjects without an effectiveness failure and who (1) do not have full 12 months of follow-up and/or sufficient follow-up duration for the primary effectiveness endpoint (i.e., with at least 335 days of follow-up or arrhythmia monitoring post the index procedure), or (2) are missing all remote arrhythmia and holter monitoring records as required by protocol will be considered missing primary effectiveness endpoint and will be excluded from the primary effectiveness analysis.

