7.4.3 Handling of Missing Data

Missing data will be queried for reasons and handled on an individual basis.

- **Sample Size Selection Interim Analysis:** For the sample size selection interim analyses, subjects with incomplete follow-up data for the effectiveness endpoint will be censored at the time of their last follow-up visit, and only their observed partial follow-up time will contribute to the estimation of model parameters and compute the predictive probability of the effectiveness success.
- **Early Success Primary Safety Endpoint:** For the early success interim analysis of the safety endpoints, if a subject's 3-month follow-up is not complete but a PAE has occurred prior to 3-month follow-up, the subject will be considered as having an event. If a subject exits the study without completing their 3-month follow-up visit and the subject has not had a PAE, that subject will be excluded from the early success safety analysis.
- **Early Success Primary Effectiveness Endpoint:** For the early success interim analysis of the effectiveness endpoints, subjects with incomplete follow-up data will be censored at the time of their last follow-up visit (if event-free). For these subjects, only their observed partial follow-up time will contribute to the estimation of model parameters. Subjects who refuse the remote arrhythmia/holter monitoring device will be excluded from the early success effectiveness analysis.

- **Final Primary Safety Endpoint:** For the final primary safety analysis, if a subject does not have full 12 months of follow-up and the subject has had a PAE at any time during the follow-up, the subject will be considered an event. If a subject does not have 12 months of follow-up but has at least 3 months of follow-up (similar to early success interim), this subject's last observed status will be carried forward for the 12-month safety endpoint as a proxy. If a subject without a PAE does not have at least 3 months of follow-up, this subject will be considered as missing the primary safety endpoint and will be excluded from the final primary safety analysis.

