10.2 Sample Size Justification

The methods described in Broglio et al.¹ will be used to determine the sample size based on the effectiveness endpoint. Sample size selection interim analyses will be performed when 180 and 255 patients are enrolled in the mITT analysis set. Predictive probabilities for trial success will be used to determine whether the sample size at the time of the interim analysis will be sufficient or

if the trial will continue to the full sample of 330. The power for testing the primary safety endpoint is greater than 80% at all sample sizes greater than or equal to 180 subjects, assuming a primary safety rate of 7% with a performance goal of 14%.

It is assumed that there is a 5% dropout rate for the safety endpoint and a 15% dropout rate for the effectiveness endpoint. The sample size will provide greater than 80% power at one-sided significance level of 2.5% for each endpoint assuming that a true safety rate of 7% and a true effectiveness rate of 65% compared to the performance goals of 14% and 50% respectively.

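### Protocol 20.4.4.4 drops event-free subjects with under 12 months of follow-up from the primary safety test, against the SAP's 3-month rule, and this takes safety power at N=180 below the stated 80%

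*Protocol*

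**What the plan says.** **Missing data, final safety analysis.** Protocol 20.4.4.4 counts any subject with a PAE as an event. If an event-free subject's "follow-up time is less than 12 months and the subject has not had a PAE, then that subject will be excluded" from the analysis. Wave II SAP 7.4.3 differs. An event-free subject is excluded only with under 3 months of follow-up; with 3 to 12 months, the "last observed status will be carried forward for the 12-month safety endpoint as a proxy". Wave I SAP 7.4.3 also sets the cut at 3 months: it excludes a subject whose "follow-up time is less than 3 months and the subject has not had a PAE".

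**Timing.** Protocol 20.4.4.2 runs the early-success safety test on 3-month follow-up and equates it with the final one. Protocol 20.4.4.3 repeats this: "The final primary safety endpoint analysis is the same analysis performed at the early success interim as all safety data is available" at that look. Wave II SAP 7.4.1.1 and 10.4 likewise state that every subject's safety outcome is known then.

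**Population.** The safety test uses mITT-Wave II, that is, "enrolled Wave II main study phase subjects who meet eligibility criteria and have had insertion of the study" catheter. This includes subjects in whom no energy was delivered. Protocol 10.3 follows those for a short time only: "Discontinued subjects will remain in follow-up for 3-months post catheter insertion".

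**Power.** Protocol 20.4.4.1: "All sample sizes from the interim sample selections will provide greater than 80% power for the primary safety endpoint", at a PAE rate of 7% or less. Wave II SAP 10.2: "The power for testing the primary safety endpoint is greater than 80% at all sample sizes greater than or equal to 180 subjects".

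**Phrenic nerve paralysis.** Protocol 8.2.1 includes it in the composite only if permanent. Table 6 requires it to be documented at 12 months or later before it counts as permanent.

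**The concern.** The protocol rule removes subjects from one side only. Events always stay and event-free subjects leave, so the denominator shrinks while the numerator does not. The observed PAE rate rises and power falls. The SAP rule does the same over 3 months instead of 12, so far fewer subjects are lost. Two governing documents therefore give different denominators, and different power, for the same primary hypothesis test in a single-arm trial against a fixed performance goal.

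The protocol rule also does not fit the rest of the protocol. A test that excludes event-free subjects short of 12 months cannot be the same test as one run on 3-month data. Event-free subjects in whom no energy was delivered leave at 3 months, so the protocol rule drops them by design.

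The second, smaller matter is completeness at the look. A paralysis with onset within 7 days that has not resolved by then can be classed neither as a PAE nor as a non-event under Table 6. The exceptions listed in SAP 7.4.1.1 (device- or procedure-related death, PV stenosis, atrio-esophageal fistula) do not cover it.

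**Working it through.** **Inputs.** True PAE rate 7%, goal 14% and sizes 180/255/330 (Wave II SAP 10.2). Beta(1,1) prior and posterior threshold 0.975 (SAP 7.4.1). Safety drop-out 5% per year (SAP 10.6.2). Stopping shares from Table 3.a.

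**Test.** With y events among n analysed, pass if Pr(p < 0.14 | Beta(1+y, 1+n−y)) > 0.975.

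**Step 1: reproduce the plan.** Let n ~ Binomial(N, 0.95), with loss unrelated to events. Power at N=180 is 82.5%, so the claim of more than 80% reproduces. Weighting the three sizes by the Table 3.a shares gives:

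| Effectiveness | Table 3.a Win Safety | Loss unrelated to events | Protocol rule | SAP rule |
|---|---|---|---|---|
| 60% | 0.9149 | 0.9147 | 0.8851 | 0.9113 |
| 62% | 0.9026 | 0.9038 | 0.8716 | 0.8997 |
| 65% | 0.8853 | 0.8832 | 0.8465 | 0.8775 |
| 70% | 0.8588 | 0.8578 | 0.8161 | 0.8496 |

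The simulations are best matched by 5% loss unrelated to events. They match neither written rule exactly, but the SAP rule is much closer.

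**Step 2: the written rules.** Take y ~ Binomial(N, p), with event-free exclusions ~ Binomial(N−y, q). Protocol rule: q = 0.05 (12 months). SAP rule: q = 1 − 0.95^0.25 = 0.0127 (3 months).

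| N | Power, protocol | Power, SAP | Type I error, protocol | Type I error, SAP |
|---|---|---|---|---|
| 180 | 0.7786 | 0.8132 | 0.0121 | 0.0156 |
| 255 | 0.9096 | 0.9425 | 0.0105 | 0.0176 |
| 330 | 0.9681 | 0.9830 | 0.0101 | 0.0181 |

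The expected observed rate under the protocol rule is 0.07 / (0.07 + 0.93 × 0.95) = 7.34%.

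**Step 3: overall power at the planning case (7%, 65%).** Weighted safety power under the protocol rule is 0.5535 × 0.7786 + 0.2854 × 0.9096 + 0.1611 × 0.9681 = 0.8465. Multiplying by the Table 3.a effectiveness power of 0.9457 gives 0.8005. The same product under the SAP rule is 0.9457 × 0.8775 = 0.8299. The product treats the two endpoints as independent. With Table 3.a's own figures it gives 0.9457 × 0.8853 = 0.8372, against 0.8395 reported.

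**Step 4: the result can change.** With N=255, 24 PAEs and 5% annual drop-out, the SAP rule analyses about 24 + 231 × 0.9873 = 252 subjects. The posterior is 0.980, a pass. The protocol rule analyses about 24 + 231 × 0.95 = 243, and the posterior is 0.967, a fail.

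**Step 5: discontinued subjects.** The documents give no rate. If a share d of 1/2/3% is assumed, q = 1 − 0.95(1−d), and power at N=180 under the protocol rule is 76.0/74.3/72.7%.

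**Step 6: open paralysis.** With 180 evaluable subjects, 16 PAEs give 0.9759 (pass) and 17 give 0.9587 (fail), so one case matters only at the boundary. Suppose a share r of subjects has a permanent paralysis that goes uncounted at the look, and the true rate is 14% (SAP rule). The false-pass probability at N=180/255/330 is 1.7/2.0/2.0% at r = 0.1% and 2.4/3.0/3.3% at r = 0.5%. It reaches 2.5% at r = 0.53/0.33/0.27%.

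**The case against.** Protocol section 20 calls its text a brief overview and leaves the planned analyses to the SAP. If the SAP rule is the one applied, power stays above 80% at N=180. The SAP also pre-specifies best-case, worst-case and tipping-point analyses for missing safety outcomes. This is a fair reason to expect little harm in practice. It does not settle the text: the protocol rule is current, and the SAP cites this protocol without declaring a departure.

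Four stronger readings are tempting, and the documents do not support them.

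- *The 12-month rule could let an unsafe device pass.* It works the other way: type I error is lower under it than under the SAP rule.
- *Overall power drops from the simulated 84.0% to 80%.* That compares two methods. On one method it goes from 83.0% to 80.1%, which still just meets the protocol's figure of above 80%. The SAP's statement that safety power exceeds 85% in every scenario also narrowly fails under the SAP's own rule, at 84.96% for 70% effectiveness.
- *The 12-month rule would be applied at the early-success look.* At N=180 with 30 subjects at 12 months, the expected observed rate would be 12.6 / (12.6 + 27.9) = 31%. The section introduces its safety rule for the final analysis, so this shows only that 20.4.4.3 and 20.4.4.4 cannot both hold.
- *Paralysis is the one outcome unknown at the look, and it threatens the error level.* Late device- or procedure-related death, PV stenosis and atrio-esophageal fistula are also PAEs and can follow the look; SAP 7.4.1.1 says so and calls the two tests nearly identical. Protocol 6.4.1 does not expect phrenic nerve injury. The events committee's charter, which is not among the documents, may cover an open case. After early success, SAP 7.4.1.2 still repeats the sensitivity analyses descriptively on 12-month data.

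**Conclusion.** The main point holds. The protocol's 12-month exclusion contradicts both SAPs, its own equation of the final and early-success safety tests, and its 3-month follow-up of discontinued subjects. It costs 3.5, 3.3 and 1.5 percentage points of safety power at N=180, 255 and 330, and about 2.9 points of overall power at the planning case. The stated safety power above 80% at every size fails at N=180, where Table 3.a expects enrollment to stop in 55% of trials at 65% effectiveness. The error is conservative: lost power and an observed rate of about 7.3% for a true 7.0%, not a false safety claim. These figures rest on the SAP's 5% annual drop-out, constant over the year and independent of PAEs.

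The paralysis point also holds, but it is small. The statements that safety outcomes are complete at the look are wrong for a case still open, and the plan does not say how to count one. The 2.5% level is exceeded only if roughly 0.3 to 0.5% of subjects have an uncounted permanent paralysis and the true PAE rate is at the 14% goal.

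**What to change.** 1. In protocol 20.4.4.4, replace the 12-month exclusion with the 3-month rule of Wave II SAP 7.4.3.
2. In protocol 20.4.4.2 and 20.4.4.3 and Wave II SAP 7.4.1.1 and 10.4, state that safety outcomes are known at the look except for (a) late-onset device- or procedure-related death, PV stenosis and atrio-esophageal fistula, which SAP 7.4.1.1 already lists, and (b) a phrenic nerve paralysis not yet documented as resolved.
3. Pre-specify how an open paralysis is counted at the look, for example as an event. This would be a conservative analysis convention that leaves the Table 6 definition unchanged.
4. After early success, report the safety posterior recomputed on all 12-month PAE data, covering the late-onset components and paralysis status, beside the interim result.

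The cost is a text amendment to the protocol and SAP, with no added scheduled assessment. If open cases count as events, the interim count may include a paralysis that later resolves, so the interim and 12-month results can differ slightly.

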20.4.4.5 Sensitivity Analyses

To investigate the robustness of the analysis result for the primary endpoints, several sensitivity analyses will be performed. Details on these analyses will be provided in SAP.

